Rash	
Some observations of rash with oral RPV have been reported in clinical studies executed to date (the majority are Grade 1 or 2).
 
Severe skin and hypersensitivity reactions have been reported during the postmarketing experience, including cases of Drug Reaction with Eosinophilia and Systemic Symptoms (DRESS), with oral RPV containing regimens. While some skin reactions were accompanied by constitutional symptoms such as fever, other skin reactions were associated with organ dysfunctions, including elevations in hepatic serum biochemistries.
	
 • Participants with a Grade 1 or 2 rash will be allowed to continue treatment or to be rechallenged, depending on the clinical judgment of the investigator. • All participants experiencing a Grade 3 or 4 rash should discontinue their antiretroviral (ARV) medication (study medication and background regimen) and be withdrawn from the study. • All rash events should be assessed with special attention to systemic symptoms, laboratory abnormalities, or mucosal involvement. Close clinical follow-up, including follow-up of laboratory abnormalities, and appropriate

Potential Risk of Clinical Significance	Summary of Data/Rationale for Risk	Mitigation Strategy
		
medical intervention, including referral to dermatologist as appropriate, should be instituted for these events; daily follow-up is recommended for 5 days from the onset of the event to monitor for progression of the event. See Section 8.7.12 for additional guidance on management of rash events.

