
DTG: Hypersensitivity reaction (HSR) and rash
 
RPV: Rash
	
DTG: HSR has been observed uncommonly with DTG. Rash was commonly reported in DTG Phase IIb/III clinical trials; episodes were generally mild to moderate in intensity; no episodes of severe rash, such as Stevens-Johnson Syndrome (SJS), Toxic Epidermal Necrolysis (TEN) and erythema multiforme were reported.
 
RPV: Rash is a recognized risk for the non-nucleoside reverse transcriptase inhibitors (NNRTI) class; however, the severe rashes defined above that are labeled for efavirenz (EFV) and nevirapine (NVP) were not seen with RPV in
	
Specific/detailed toxicity management guidance is provided for HSR (Section 8.7.11) and rash (Section 8.7.12).
 
The subject informed consent form includes information on this risk and the actions subjects should take in the event of: 1) a HSR or associated signs and symptoms; or 2) developing any type of rash or skin abnormality. For Grade 3/4 rash, except where the etiology is clear and not associated with study drug or where there is a definitive diagnosis clearly attributable to a concomitant medication

Potential Risk of Clinical Significance	Data/Rationale for Risk	Mitigation Strategy ^a
Commercial Juluca [DTG and RPV] Refer to IBs for additional information		
	clinical trials. In Phase III clinical trials, skin events of interest were reported at a lower incidence and grades, and resulted in fewer subject withdrawals, in the RPV group than in the EFV group and were mostly driven by the individual preferred term Rash.	(and not to study drug) or to a concomitant infection, subjects must permanently discontinue study drug and be withdrawn from the study.

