- Renal toxicity is met and no compelling alternate cause is identified;
- Corrected QT interval (QTc) >550 msec from three or more tracings separated by at least 5 minutes and considered causally related to IP. *Note: ECGs are not routinely conducted in this study.*
- Grade 4 clinical AE considered causally related to study drug;
- Participant has a Grade 3 or higher rash or Grade 2 rash with evidence of systemic involvement and no compelling alternative cause is identified
- Pregnancy (intrauterine), regardless of termination status of pregnancy.
- Participant withdrew consent

Efficacy data for participants withdrawing from the study will be considered evaluable up to the point at which they are withdrawn using the same criteria for evaluability as for participants who complete the study.

Safety data for all participants who receive any amount of study drug, including participants who withdraw from the study, will be included in evaluations of safety.

If a participant is prematurely or permanently withdrawn from the study, the procedures described in the Time and Events Table for the in-clinic Withdrawal visit are to be performed. An in-clinic Follow-Up visit will be conducted 4 weeks after the last dose of study medication for participants with ongoing AEs, and serious adverse events (SAEs) related & not related to study drug and also any laboratory abnormalities that are considered to be AEs or potentially harmful to the participant, at the last on-study visit.

All data from the Withdrawal visit will be recorded, as they comprise an essential evaluation that should be done prior to discharging any participant from the study.

The following actions must be taken in relation to a participant who fails to attend the clinic for a required study visit:

- a. The site must attempt to contact the participant and re-schedule the missed visit as soon as possible.

- b. The site must counsel the participant on the importance of maintaining the assigned visit schedule and ascertain whether or not the participant wishes to and/or should continue in the study.
- c. In cases where the participant is deemed ‘lost to follow up’, the investigator or designee must make every effort to regain contact with the participant (where possible, 3 telephone calls and if necessary a certified letter to the participant’s last known mailing address or local equivalent methods). These contact attempts should be documented in the participant’s medical record.

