Rash is an adverse drug reaction (ADR) for RPV. In clinical trials, most rashes emerged during the first 4 weeks of treatment, were transient, and usually mild (Grade 1) to moderate (Grade 2). There were no Grade 4 rashes and none were serious. Treatment-related Grade 3 rash was reported in 0.1% of participants in the RPV group. Treatment-related rash led to permanent discontinuation in 0.1% of participants in the RPV group. No cases of erythema multiforme, SJS or TEN have been reported during clinical development of RPV.

Participants with an isolated Grade 1 rash may continue study drug at the Investigator's discretion. The participant should be advised to contact the Investigator immediately if there is any worsening of the rash, if any systemic signs or symptoms appear, or if mucosal involvement develops.

Participants may continue study drug for an isolated Grade 2 rash. However, study drug (and all other concurrent medication(s) suspected in the Investigators causality assessment) should be permanently discontinued for any Grade ≥ 2 rash that is associated with an increase in ALT. The participant should be advised to contact the physician immediately if rash fails to resolve (after more than 2 weeks), if there is any worsening of the rash, if any systemic signs or allergic symptoms develop, or if mucosal involvement develops.

Participants should permanently discontinue study drug [and all other concurrent medication(s) suspected in the Investigators causality assessment] for an isolated Grade 3 or 4 rash, except where the etiology of the rash has been definitively diagnosed as NOT attributable to study drug (see below), and the participant should be withdrawn from the study. Participants should be treated as clinically appropriate and followed until resolution of the AE. Every effort should be made to collect as much information as possible about the evolution of the event and any relationship with potentially related medical events (e.g., viral infection) or start of concomitant medication.

The rash and any associated symptoms should be reported as adverse events and appropriate toxicity ratings should be used to grade the events (based on DAIDS toxicity gradings – see Section 12.3, Appendix 3).

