However, if the etiology of the rash has been definitively diagnosed as being unrelated to study drug and due to a specific medical event or a concomitant infection or a concomitant non-study medication, routine management should be performed and documentation of the diagnosis provided. In this situation, the study drug should be continued.

Participants in the Follow-Up Phase who are receiving ABC as part of their regimen should be evaluated for the possibility of a clinically suspected ABC HSR and managed appropriately as outlined in the local prescribing information for ABC.

Any participant receiving at least one dose of CAB LA and /or RPV LA who discontinue IP / Withdraw will initiate treatment with HAART and enter the LTFU Phase for 52 weeks of follow-up.

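### The protocol gives opposite instructions for a Grade 3 or 4 rash of unrelated cause: Section 2.3.1 (RPV LA) stops everyone, Section 8.7.12 continues study drug

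*Protocol*

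**What the plan says.** Four places in the protocol tell a site what to do about rash.

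- **Section 2.3.1, RPV LA table, Rash row.** For severe rash: "All participants experiencing a Grade 3 or 4 rash should discontinue their antiretroviral (ARV) medication (study medication and background regimen) and be withdrawn"; the withdrawal meant is from the study. Cause is not mentioned. For Grade 1 or 2, continuing or rechallenging is left to the investigator. The row then asks for attention to systemic signs and laboratory findings, and adds: "See Section 8.7.12 for additional guidance on management of rash events".
- **Section 2.3.1, DTG + RPV table, rash row.** Permanent discontinuation and withdrawal are required, but with an exception: "For Grade 3/4 rash, except where the etiology is clear and not associated with study drug", or where a concomitant medication or infection has been definitively diagnosed as the cause.
- **Section 7, list of reasons for which study intervention must stop.** "Participant has a Grade 3 or higher rash or Grade 2 rash with evidence of systemic involvement and no compelling alternative cause is identified".
- **Section 8.7.12.** Study drug is permanently discontinued and the participant withdrawn "for an isolated Grade 3 or 4 rash, except where the etiology of the rash has been definitively diagnosed as NOT attributable to study drug". Where such a diagnosis exists, "In this situation, the study drug should be continued". Permanent discontinuation also follows any Grade 2 or higher "rash that is associated with an increase in ALT". Participants who have had a long-acting dose and stop "will initiate treatment with HAART and enter the LTFU Phase for 52 weeks of follow-up".

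**The concern.** A stopping rule should give the same answer wherever a site looks it up. Here an investigator who reads the RPV LA risk row and one who reads Section 8.7.12 would do opposite things for the same participant, and both could say they followed the protocol.

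For that participant, an effective regimen may be stopped or continued depending on which section was read. For the analysis, the proportion who discontinue treatment because of adverse events is a secondary endpoint, and a stop before Month 12 can change the Snapshot category.

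**Working it through.** The protocol states no figure for this rule, so the check sets the texts side by side and then traces the effect on the endpoints.

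**1. Isolated Grade 3 or 4 rash, cause definitively unrelated**

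| Place | Cause exception | Result |
|---|---|---|
| 2.3.1, RPV LA | None | Stop all antiretrovirals; withdraw |
| 8.7.12 | Definitive diagnosis of another cause | Continue study drug |
| Section 7 | Compelling alternative cause | Depends on reading (below) |
| 2.3.1, DTG + RPV (that regimen only) | Clear unrelated etiology, or definitive diagnosis of a concomitant medication or infection | Mandatory stop not triggered |

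The first two rows are opposite actions. The pointer from the RPV LA row to 8.7.12 offers further guidance; it does not make the row subject to 8.7.12. The RPV LA row also names a background regimen, although Section 6.2 gives the long-acting participants none besides CAB LA + RPV LA.

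The Section 7 bullet can be read two ways. If its qualifier on cause covers the whole bullet, it agrees with 8.7.12 that an exception exists but sets a different standard of proof. If the qualifier covers only the Grade 2 part, Section 7 requires a stop where 8.7.12 continues. Either way it needs reconciling.

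**2. Grade 2 rash**

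- 2.3.1 (RPV LA): investigator judgment, unqualified.
- Section 7: stop if there is systemic involvement and no compelling alternative.
- 8.7.12: an isolated rash may continue, but any associated ALT rise means a permanent stop. No ALT threshold is given.

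The ALT trigger is not in Section 7's rash bullet. The liver criterion in Section 7.1.1 that names rash as a symptom starts at 3 times the upper limit of normal, or 3 times baseline if baseline ALT was raised. A Grade 2 rash with a smaller rise is therefore a permanent stop in one place and a matter of judgment in another.

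**3. Effect on the Month 12 Snapshot**

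Inputs for the long-acting arm, from the SAP: the Month 12 window is Days 285 to 375 (Table 8); on-treatment status lasts to the last injection + 67 days if there is no later oral CAB + RPV (Table 15); the Maintenance Phase ends when LTFU ART starts (Table 13).

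A viral load can count only if last injection day + 67 ≥ 285, so the last injection must be on Day 285 − 67 = 218 or later. Using the target days in Table 6:

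- last injection at Month 8 (Day 211): 211 + 67 = 278, before the window opens, so no value can count;
- last injection at Month 10 (Day 271): 271 + 67 = 338, so a value from Day 285 to Day 338 still counts, if taken no later than the start of LTFU ART.

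With no countable value, SAP Appendix 9 (step 5.2.2.1) places a safety withdrawal in No virologic data. The participant stays in the denominator, is lost from the secondary <50 c/mL count if otherwise suppressed, and is not added to the primary ≥50 c/mL count.

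**4. Size**

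- Enrolment is about 100 across two self-selected arms, and the split is not given. One case is 1/100 = 1.0 percentage point if all chose the long-acting arm; with an assumed 80 it is 1.25 points, and with an assumed 50 it is 2.0.
- For scale, adverse-event withdrawals on Q8W dosing in LATTE-2 were 2 of 115 = 1.7% (reported as 2%). That is through Week 96, a longer period than Month 12.
- Section 8.7.12 cites 0.1% treatment-related Grade 3 rash for RPV: 0.001 × 100 = 0.1 participant. The rules diverge on unrelated rash, for which the protocol gives no rate.

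**The case against.** The strongest reply has four parts.

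- **Status of the text.** The RPV LA row sits in an introductory risk table, says should rather than must, and points to 8.7.12. Section 6.8 also requires decisions on dose interruption and resumption to be discussed with the medical monitor in advance. This makes opposite decisions less likely in practice, but the instruction still reaches every participant with no exception for cause.
- **Grade 2.** The rules are mostly cumulative: 8.7.12 deals with rash alone, Section 7 adds systemic involvement, and a site can apply both plus the ALT trigger. This largely stands, so Grade 2 is the secondary point. What remains is the unqualified permission in the RPV LA row and the ALT trigger missing from Section 7.
- **Exception standards.** The DTG + RPV row, read in full, comes close to 8.7.12 and concerns the other regimen. That is fair, but its clear-etiology limb and the Section 7 wording still set different tests.
- **Endpoint effect.** Stopping does not automatically lose the Month 12 result. That stands, as step 3 of the working shows.

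A reader might also infer that a long-acting participant stopped under Section 2.3.1 would be left without antiretroviral therapy and outside long-term follow-up. The documents do not support that. The next row of the same RPV LA table provides HAART within 8 weeks of the last dose and at least 52 weeks of monitoring. Sections 4.2.3, 7.1, 8.1.3 and 8.7.12 send long-acting participants who stop or withdraw into follow-up. Section 8.7.12 itself pairs withdrawal from the study with LTFU entry, so withdrawal does not mean leaving follow-up.

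**Conclusion.** The conflict is real and narrow. For a Grade 3 or 4 rash with a definitively unrelated cause, the RPV LA row of Section 2.3.1 and Section 8.7.12 direct opposite actions, and the other two places express the exception differently. The Grade 2 mismatch is secondary.

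The expected effect is small: few participants, each worth at least about 1 percentage point of the long-acting arm's adverse-event discontinuation rate. A Snapshot change is conditional on having no on-treatment viral load in the Month 12 window, and it would be to No virologic data, not to HIV-1 RNA ≥50 c/mL. The sample size and precision figures are unaffected.

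This assumes that the stop is recorded as a safety reason and that HAART started afterwards is handled as LTFU therapy. SAP Appendix 9 would count a change of ART during Maintenance as ≥50 c/mL. No view is taken on which clinical rule is right.

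**What to change.** The sponsor should reconcile the RPV LA and DTG + RPV rash rows of Section 2.3.1, the rash bullet in Section 7 and Section 8.7.12 into one rule per grade. That rule needs:

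- one standard for accepting an alternative cause, and a clear statement of which grades it covers;
- one definition of what forces a stop at Grade 2, including whether and how ALT enters, listed in Section 7 as well as in 8.7.12.

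The Section 2.3.1 tables should then refer to that rule instead of restating it. The content of the rule is for the sponsor to decide. The cost is protocol wording; nothing in the SAP needs to change.

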2.3.1.1. Other Clinically Relevant Information

Additional details concerning safety observations from clinical studies and for which a causal association has not been established or which are of minimal clinical significance may be found in the Investigator's Brochures (GlaxoSmithKline Document Number [RH2009/00003/07](#) [CAB IB, 2017], [RPV IB](#), 2017, GlaxoSmithKline Document Number [RM2007/00683/11](#) [DTG IB, 2017]).

Adverse Events of Special Interest:

Seizure

Four cases of seizures have occurred in the cabotegravir programme cumulatively through 04 May 2018 (update Date). Two of the cases occurred in HIV uninfected subjects with a prior history of seizure, of which one had CAB drug levels below the level of quantification 6 months prior to the event and one case involved a subject in study 200056 with circumstantial and anecdotal evidence of illicit drug use. Another case occurred in FLAIR in the context of influenza A meningoencephalitis. Overall, there is not convincing evidence that cabotegravir exposure may be causally associated with seizure or with reduction of seizure threshold, due to the low frequency of reports, the confounders present in the cases received to date and lack of any pre-clinical signal or identified plausible mechanism. However, seizure and seizure-like events are considered as AEs of special interest for close monitoring in studies. Subjects with an unstable or poorly controlled seizure disorder will be excluded from study participation.

2.3.2. Benefit Assessment

The antiviral activity against HIV-1 of CAB has been well established through Phase 2a and Phase 2b studies. RPV is an established antiviral agent against HIV-1 in treatment naive participants, with long term durability (>96 weeks in Phase 3 and >240 weeks in Phase IIb).

Participants receiving CAB LA + RPV LA are anticipated to benefit from maintenance of virological suppression using LA agents. Participants who receive CAB LA+ RPV LA Q2M dosing will not need to take concomitant daily oral therapy. Adherence in these participants is expected to be improved and will be directly observed during IM injections. Efficacy of this two-drug regimen, as IM agents, has been demonstrated through Week 96 of the ongoing 200056 study. This regimen may continue to offer long term safety and tolerability benefits in these participants.

Participants who will receive PO DTG and RPV are anticipated to benefit from the fact that both are conveniently dosed as a single tablet once daily, without need for a pharmacokinetic (PK) booster, and with limited safety implications resulting from theoretical or actual drug:drug interactions compared to other ART agents (including efavirenz (EFV) and those requiring a PK booster). In addition, the high barrier to resistance observed with DTG should help protect against the development of resistance to both components of the DTG + RPV regimen. Juluca was recently approved as single dose maintenance. Individually, DTG and RPV in combination with other ARVs have demonstrated durable virologic and immunologic response.

2.3.3. Overall Benefit: Risk Conclusion

Taking into account the measures taken to minimize risk to participants participating in this study, the potential risks identified in association with the CAB LA and RPV LA Q2M and DTG + RPV regimens and the study as a whole are justified by the anticipated benefits that may be afforded to virologically suppressed, treatment-experienced participants with HIV-1 infection.

3. OBJECTIVES AND ENDPOINTS

Objectives	Endpoints
Primary	
To demonstrate the antiviral activity of CAB LA + RPV LA every 2 months in suppressed HIV-1 infected antiretroviral therapy ART-experienced participants	Proportion of participants with HIV-RNA ≥ 50 c/mL as per food and drug administration (FDA) Snapshot algorithm at Month 12
Secondary	
To demonstrate the antiviral and immunologic activity of CAB LA + RPV LA every 2 months and oral DTG +RPV	Proportion of participants with plasma HIV-1 RNA <50 c/mL (c/mL) at Month 12

Objectives	Endpoints
once daily	
using the FDA Snapshot algorithm
 
Proportion of participants with protocol-defined confirmed virologic failure (CVF) over time
 
Proportion of participants with HIV-RNA greater than or equal to 50 c/mL as per FDA Snapshot algorithm over time
 
Absolute values and changes from Baseline in viral load and CD4+ cell counts over time

To demonstrate the safety and tolerability of CAB LA + RPV LA every 2 months and oral DTG + RPV once daily	
Incidence and severity of AEs and laboratory abnormalities over time
 
Proportion of participants who discontinue treatment due to AEs over time
 
Change from Baseline in laboratory parameters over time

To assess viral resistance in participants experiencing protocol-defined confirmed virologic failure	Incidence of treatment emergent genotypic and phenotypic resistance to CAB, RPV, and DTG + RPV
To characterize CAB and RPV concentrations and population pharmacokinetics and identify important determinants of variability	Plasma PK parameters for CAB LA and RPV LA (when evaluable, trough concentrations [C_{trough}])
To assess participant reported health-related quality of life, injection tolerability/acceptability, and treatment satisfaction.	
Change from Baseline (Day 1) in HIVDQoL at Months 6 and 12 (or Withdrawal)
 
Change from baseline (Day 1) in total “treatment satisfaction” score, and individual item scores of the HIV Treatment Satisfaction Status Questionnaire (HIVTSQs) at Months 6 and 12 (or Withdrawal)
 
Change in treatment satisfaction over time using the HIV Treatment Satisfaction Change Questionnaire HIVTSQc at Month

Objectives	Endpoints
	12 (or Withdrawal).
Exploratory	
Explore the concept of a digital assistance program and the effect on participant participation and adherence to timeliness of injections given every 2 months	The number of participants who utilize the program Adherence to scheduled date of injection
To assess reason for switching using a single question. To assess preference using a single question	The ‘Preference’ question will be used to assess preference for CAB LA + RPV LA every 2 months compared to prior oral CAB + RPV regimen, at Month 12 using a single dichotomous preference question. The ‘Reason for Switch’ question will be administered at Day 1 (Baseline) to assess the reasons for willingness to switch to LA injectable ART.

